### 6.8.2 Prohibited Concomitant Medications

Concomitant anticancer therapies of any kind including extensive non-palliative radiation are not permitted. Immunosuppressive doses of systemic corticosteroids are prohibited (unless utilized to treat a drug-related AE).

### 6.8.3 Imaging Restrictions and Precautions

Tumor evaluation by CT or MRI will be conducted according to RECIST v1.1 in accordance with the schedule of assessments. Patients with a heart pacemaker, brain aneurysm clips, and some implanted metallic or electrical devices should not have an MRI. Patients with known allergies or discomfort from contrast agents may have imaging without contrast.

## 6.9 Dose Modifications

### 6.9.1 Dose Escalation

The algorithm for dose escalations is described in [Table 6](#). Intra-patient dose escalation will be permitted in patients enrolled at dose levels below 70 mg provided the criteria in Section [4.1.1.5](#) are met.

Safety will be monitored throughout the study by the Sponsor's CRC, comprised of Phase 1a study investigators, the Sponsor's medical monitor, and the Sponsor's safety representative. The CRC will meet routinely to review the emerging safety, PK, pharmacodynamics, and efficacy data, and to make dose escalation decisions.

In Phase 1a dose exploration, patients will be enrolled at one or more dose levels from Phase 1a, and dose escalation will not be permitted.

In Phase 1b, patients will be treated at the MTD and/or RD as determined from Phase 1a dose escalation, and dose escalation will not be permitted.

### 6.9.2 Toxicity at Lowest Dose Level

If the MTD is unexpectedly exceeded at the first dose level of FPT155 (0.07 mg), dosing will be suspended. Decisions on how to next proceed including decision on evaluating a lower dose will be based on safety, tolerability, and PK data, and will be determined by the CRC (refer to Section [4.1.1](#)).

### 6.9.3 Dose Modification and Delay Criteria

Dose reductions or delays for FPT155 may be permitted for patients on treatment beyond the DLT evaluation interval in Phase 1a dose escalation, any patients in the Phase 1a dose exploration, or any patients in Phase 1b per the guidelines in [Table 9](#). Dose reductions can be assessed using local laboratories. If a patient in Phase 1a dose escalation requires a dose reduction of FPT155 during the DLT period, they will be considered a DLT and be permanently discontinued from FPT155.

Dose reductions and delays for FPT155-related AEs or laboratory abnormalities should follow the guidelines outlined in [Table 9](#). Refer to Section [6.9.4](#) and [Appendix 10](#) for additional specific guidelines for irAEs and CRS. Any variations from these guidelines must be discussed with the Sponsor prior to dosing and must take into consideration the overall benefit and risks for the patient of continued participation in the study.

**Table 9: Dose Modification and Delay Criteria for FPT155 (Non-Infusion Toxicity)**

FPT155-related Toxicity Grade	Dose Schedule	New FPT155 Dose
Grade 1	No delay or missed dose required	100% of dose
Grade 2	Delay or miss dose until recovery to Grade 1 for suspected irAEsa and CRSb No delay or missed dose required for other AEs	100% of dose
Grade 3 (first occurrence)	Delay or miss dose until recovery to baseline or Grade 1	If recovery to baseline or Grade 1 within 14 days, may resume at 100% of starting dose or 1 dose lower c
Grade 3 (second occurrence)	Delay or miss dose until recovery to baseline or Grade 1	If recovery to baseline or Grade 1 within 14 days, may resume at 1 level lower b than previous dose or discontinue
Grade 3 (third occurrence) Grade 3 which does not recover to baseline or Grade 1 within 14 days Any Grade 4	Permanently Discontinue	N/A

a Refer to Section 6.9.4 and [Appendix 8](#) for additional guidance regarding irAEs

b Refer to Section 6.9.5 and [Appendix 10](#) for additional guidance regarding CRS

c E.g., 1 dose level lower for patients treated at 70.0 mg is 42.0 mg; 1 dose level lower for patients treated at 42.0 mg is 21.0 mg.

Abbreviations: AE = adverse event; irAEs = immune-related adverse events; CRS = cytokine release syndrome.

The first dose of each cycle is considered Day 1 of each cycle. Cycles will repeat every 21 days unless there is a treatment delay. A treatment delay of longer than 4 weeks should be discussed with the medical monitor prior to continuation of that subject on study. Treatment is administered Q3W until disease progression, unacceptable toxicity, or until the patient meets any of the other protocol-specified withdrawal criteria.

#### 6.9.4 Management of irAEs

Based on the underlying mechanism action, irAEs associated with the anti-CTLA-4 class of drugs (eg, ipilimumab) may potentially be observed with FPT155. Given the differentiated mechanism of action of FPT155 and the absence of any clinical data, the actual timing, incidence and severity of these AEs may differ significantly from anti-CTLA-4 therapies. General guidelines for management of suspected irAEs are provided here. These may be supplemented by discussions with the Sponsor as well as institutional guidelines on management of these toxicities.

In all instances, patients should be thoroughly evaluated to rule out a non-inflammatory etiology (eg, disease progression, concomitant medication, infections etc.). Symptomatic or topical therapy should be considered for most Grade 1 or 2 events unless otherwise specified in [Appendix 8](#). Corticosteroids are the primary therapy for irAEs. Corticosteroids should be tapered over at least 2-4 weeks in patients experiencing Grade 2 AEs and at least 4-8 weeks in

patients experiencing Grade 3/4 AEs. Appropriate antiviral, antifungal (e.g. pneumocystis) and antibacterial prophylaxis must be considered in patients receiving corticosteroids for prolonged durations to reduce the risk of opportunistic infections. More potent immunosuppressive agents such as TNF inhibitors (eg, infliximab) should be considered for events not responding to systemic steroids. Refer to [Appendix 8](#) for additional specific guidelines for individual irAEs.

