### Immune-related hepatotoxicity

#### Incidence

Hepatitis occurs in 5%–10% (of which 1%–2% is grade 3) of patients during therapy with ipilimumab, nivolumab and pembrolizumab at the approved doses as single agents and in ~25%–30% (of which ~15% is grade 3) of those treated with the combination of ipilimumab 3 mg/kg and nivolumab 1 mg/kg [2, 12].

[figure not shown]

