### Management

In the event of moderate (grade 2) transaminase or total bilirubin elevation, checkpoint inhibitor therapy should be withheld and transaminases and bilirubin measured twice weekly. Persistent grade 2 elevation lasting longer than 1–2 weeks, after having ruled out other causes, should be treated with corticosteroids at a dose of 1 mg/kg/day (methyl)prednisolone or equivalent. Upon improvement, checkpoint inhibitor therapy may be resumed after corticosteroid tapering. If worsening or no improvement occurs despite initiation of corticosteroids, corticosteroid dose should be increased to 2 mg/kg/day (methyl)prednisolone or equivalent and checkpoint inhibitor therapy permanently discontinued [IV–V, B]. For grade 3 or 4 transaminase or total bilirubin elevation, checkpoint inhibitor therapy should be permanently discontinued, and corticosteroids started at 1–2 mg/kg/day (methyl)prednisolone or equivalent. If there is no response to corticosteroids within 2–3 days, mycophenolate mofetil should be added at 1000 mg twice daily [IV–V, B] [34]. Consultation with a hepatologist and consideration of liver biopsy (see above) is recommended in steroid and mycophenolate-refractory cases

**Figure 6.** ICPi-related toxicity: management of hypophysitis.

\*Pituitary Axis bloods: 9 am cortisol (or random if unwell and treatment cannot be delayed), ACTH, TSH/FT4, LH, FSH, oestradiol if premenopausal, testosterone in men, IGF-1, prolactin. Mineralocorticoids replacement is rarely necessary in hypopituitarism.

\*\*Initial replacement advice for cortisol and thyroid hormones:

- If 9 am cortisol < 250 or random cortisol < 150 and vague symptoms:
  - Replace with hydrocortisone 20/10/10 mg
  - If TFTs normal, 1–2 weekly monitoring initially (always replace cortisol for 1 week prior to thyroxine initiation)
- If falling TSH +/- low FT4
  - Consider need for thyroxine replacement (guide is 0.5–1.5 µg/kg) based on symptoms +/- – check 9 am weekly cortisol
  - See Thyroid Guidelines for further information regarding interpretation of an abnormal TSH/T4

ACTH, adrenocorticotrophic hormone; FSH, follicle-stimulating hormone; FT4, free thyroxine; HRT, hormone replacement therapy; ICPi, immune checkpoint inhibitor; IGF-1, insulin-like growth factor-1; IM, intramuscular; i.v. intravenous; LH, luteinizing hormone; MRI, magnetic resonance imaging; NSAIDs, nonsteroidal anti-inflammatory drugs; od, once daily; TSH, thyroid-stimulating hormone; TFTs, thyroid function tests.

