[IV–V, B]. Third-line immunosuppressive therapy is not well defined but the successful use of anti-thymocyte globulin (ATG) has been reported in a case of ipilimumab-induced hepatitis refractory to steroids and mycophenolate. Another third-line immunosuppressive therapy option is tacrolimus. Infliximab is not recommended for the treatment of immune-related hepatitis (see Figure 7).

[figure not shown]
Hepatitis usually resolves within 4–6 weeks with appropriate treatment but in the event that it does not resolve, other contributory causes should be reconsidered and the initial diagnostic work repeated as necessary, particularly bearing in mind the concomitant administration of other hepatotoxic drugs (including herbal medications and those purchased over the counter) and cytomegalovirus (CMV) reactivation.

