**Immune-related hepatotoxicity**

- For grade 2 hepatitis, withhold ICPI and monitor AST/ALT levels closely (1–2 times/week). When no improvement over 1 week, start (methyl)prednisolone (0.5–1 mg/kg). Taper over several weeks under close monitoring of AST/ALT and bilirubin [IV–V, B].
- For grade 3 hepatitis, discontinue ICPI and immediately start with (methyl)prednisolone 1–2 mg/kg. When no improvement in 2–3 days, add MMF (1000 mg 3 x daily). Taper immunosuppression over 4–6 weeks under close monitoring of AST/ALT and bilirubin [IV–V, B].
- For grade 4 hepatitis, permanently discontinue ICPI, admit patient to the hospital and initiate (methyl)prednisolone 2 mg/kg i.v. Add MMF if no improvement is observed within 2–3 days. Consult hepatologist if no improvement under double immunosuppression. Other immunosuppressive drugs to consider are ATG and tacrolimus. Consult or refer patient to an experienced centre. Taper over 6 weeks under close monitoring of liver tests [IV–V, B].

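### Section 6.9.4 names infliximab as the example drug for steroid-refractory immune-related events without excepting hepatitis, for which the guideline attached as Appendix 9 advises against it and adds mycophenolate mofetil

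*Protocol*

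**What the plan says.** Protocol Section 6.9.4 presents itself as general guidance on suspected irAEs. Corticosteroids are the primary therapy. If they fail, "More potent immunosuppressive agents such as TNF inhibitors (eg, infliximab) should be considered for events not responding to systemic steroids". The section then refers to Appendix 8 "for additional specific guidelines for individual irAEs". It also allows supplementation by discussion with the sponsor and by institutional guidelines.

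For Grade 3/4 hepatitis, Appendix 8 specifies permanent discontinuation of FPT155, liver function tests every 1–2 days, intravenous methylprednisolone or equivalent, referral to a hepatologist and liver imaging, with biopsy to be considered at Grade 4. It names no drug after steroids. Its introduction says that the tables are adapted from the guideline reproduced in Appendix 9. It sends the reader to that guideline for irAEs that the tables do not cover.

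Appendix 9, in its hepatotoxicity section, states: "Infliximab is not recommended for the treatment of immune-related hepatitis". For Grade 3 or 4 elevations the second step is MMF: "If there is no response to corticosteroids within 2–3 days, mycophenolate mofetil should be added at 1000 mg twice daily". Table 2 of the same guideline repeats the step for Grade 3 at a different frequency, "When no improvement in 2–3 days, add MMF (1000 mg 3 x daily", and for Grade 4 without a dose, "Add MMF if no improvement is observed within 2–3 days".

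**The concern.** Applied to hepatitis that does not respond to steroids, the only drug class and the only drug named as examples in 6.9.4 are ones that the protocol's own attached source advises against for that organ. Following the cross-references does not put this right. Appendix 8 says nothing on the matter, and its pointer to Appendix 9 does not reach hepatitis, because Appendix 8 does discuss hepatitis.

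Section 2.4 lists hepatitis among the irAEs that may be seen with FPT155. For the combination with pembrolizumab, the same section relies on the consensus guidance in Appendix 8 as a safeguard. At stake is the choice of second-line immunosuppressant in a patient with serious, steroid-refractory liver toxicity. No endpoint, sample size or analysis in the protocol or SAP depends on it.

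**Working it through.** The plan gives no figure to reproduce, so the check is a comparison of texts.

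**Step 1: the general rule.** Section 6.9.4 covers events that do not respond to systemic steroids. It names TNF inhibitors, with infliximab as the example, and excepts no organ.

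**Step 2: the organ tables in Appendix 8.**

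| Table and grade | Drug named after steroids |
|---|---|
| Colitis, Grade 3/4 | Infliximab |
| Pneumonitis, Grade 3/4 | Infliximab, or other immunosuppression including MMF |
| Hepatitis, Grade 3/4 | None |
| Renal, Grade 4 | None |
| Skin, Grade 3/4 | None |
| Severe hypophysitis | None |

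Several rows stop at steroids, so silence alone does not set hepatitis apart.

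**Step 3: the source guideline in Appendix 9.** Its readable text names infliximab as an option for colitis, pneumonitis, cardiac toxicity and severe arthritis. Hepatitis is the only irAE for which that text advises against infliximab. The guideline's flow-chart figures are not readable here, so this comparison rests on its text and tables.

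**Step 4: the route a reader takes.** Section 6.9.4 leads to the Appendix 8 hepatitis row, which has no step for steroid failure. The Appendix 8 pointer to Appendix 9 is limited to irAEs not covered in Appendix 8. In the main text and Appendix 8 together, the general sentence in 6.9.4 is therefore the only guidance on a second drug for FPT155-related hepatitis.

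**Step 5: can the number affected be derived?** It would be patients treated × hepatitis rate × share refractory to steroids × share then given infliximab. The last two terms appear nowhere in the documents. Even the hepatitis term is unstable:

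- Planned numbers (Section 9.2): 58 + 50 + 240 = 348 on monotherapy, 30 + 30 = 60 on the combination, 408 in all.
- Class rates (Appendix 9): "Hepatitis occurs in 5%–10% (of which 1%–2% is grade 3) of patients during therapy with ipilimumab, nivolumab and pembrolizumab", and "in ~25%–30% (of which ~15% is grade 3) of those treated with the combination" of ipilimumab and nivolumab.
- If the Grade 3 figures are shares of treated patients, monotherapy gives 348 × 1% = 3.5 to 348 × 2% = 7.0 Grade 3 cases.
- If they are shares of hepatitis cases, monotherapy gives 348 × 5% × 1% = 0.2 to 348 × 10% × 2% = 0.7.
- The 240 assumes all eight Phase 1b cohorts. Appendix 11 opens five, so 5 × 30 = 150, monotherapy is 58 + 50 + 150 = 258, and the first reading falls to 2.6–5.2.

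These are counts of Grade 3 hepatitis, on the assumption that FPT155 behaves like the approved checkpoint inhibitors. They are not counts of patients exposed to the conflict.

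**Step 6: the MMF dose.** Appendix 9 gives 1000 mg twice daily in its text (2 × 1000 = 2000 mg a day) and 1000 mg three times daily in Table 2 for Grade 3 (3 × 1000 = 3000 mg a day). Any added step has to choose one.

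**The case against.** The strongest reply is that there is no direct contradiction. Section 6.9.4 is labelled general, the class it asks investigators to consider is more potent immunosuppressants, and TNF inhibitors and infliximab appear only as examples. An investigator who adds MMF satisfies both 6.9.4 and Appendix 9. This stands. A reader might infer that the protocol directs infliximab for hepatitis, or that the two texts cannot both be followed. The wording supports neither inference.

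Other safeguards also stand:

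- Appendix 8 names infliximab for colitis and pneumonitis but never for hepatitis.
- Appendix 8 calls for hepatologist referral at Grade 3/4. Appendix 9 recommends that consultation only once steroids and MMF have failed, so under this protocol a specialist should already be involved when a second drug is chosen.
- Sponsor and institutional guidance may supplement the tables.
- For irAEs associated with pembrolizumab, Section 6.9.6.2 adds the local package insert, which is not among the documents.
- The warning against infliximab is printed within the protocol, in Appendix 9.

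These points reduce the risk without correcting the text. The package insert does not help monotherapy patients, who are 348 of the 408 planned. The warning sits where the cross-references do not lead for this organ.

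**Conclusion.** The point holds as a missing exception. A general, permissive rule names as its only example a drug that the protocol's attached source advises against for hepatitis, and the hepatitis row that should refine the rule has neither a caution nor a step for steroid failure. No passage gives a reason for departing from the source.

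The size cannot be quantified. A reader might multiply the class rates by the planned numbers and treat the result as an upper bound. The documents do not support that. Depending on how one sentence is read, and on whether the ipilimumab plus nivolumab rate is applied to the combination arm, the Grade 3 total runs from 408 × 5% × 1% = 0.2 to 348 × 2% + 60 × 15% = 16.0, roughly an 80-fold spread. Nor is the top figure a ceiling on cases reaching a second drug: it leaves out Grade 4 cases and persistent Grade 2 cases, which Appendix 9 also treats with steroids. Section 6.9.4 itself warns that incidence may differ from that of the anti-CTLA-4 class.

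This is a minor patient-safety wording correction. It has no consequence for endpoints or analyses.

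**What to change.** - **Section 6.9.4:** add to the infliximab sentence: *except immune-related hepatitis, for which infliximab is not recommended*.
- **Appendix 8, Grade 3/4 hepatitis, management cell:** add: *infliximab not recommended; add MMF if no steroid response in 2–3 days*. The sponsor should state a single MMF dose, since Appendix 9 gives two.

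The change is one phrase and one table cell; visits, sample size and analyses are untouched. It does alter protocol text, so Section 10.1.3 requires a written amendment with IRB/IEC approval (and health authority approval where applicable) before implementation. It can be included in the next amendment.

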### **6.9.5 Management of CRS**

Refer to [Appendix 10](#) for specific guidelines for grading and management of CRS.

### **6.9.6 Dose Interruptions During Study Treatment Administration**

#### **6.9.6.1 FPT155**

Infusion of FPT155 must be stopped if any AE  $\geq$  Grade 3 occurs during the infusion.

If bronchospasm or dyspnea occurs in a patient during the infusion, the infusion must be stopped.

In addition, at the investigator's discretion, the infusion rate for FPT155 may be reduced or stopped if a less severe AE (Grade 1 or 2) occurs during the infusion. If a Grade 3 or less severe AE resolves within 4 hours, the infusion may be restarted at half the previous rate and promptly managed according to the discretion of the Investigator. If the same AE appears again with the same severity at any time during the restarted infusion, the infusion should be discontinued, and no further dosing of FPT155 will occur without consultation with the Sponsor or Sponsor's designee.

If a patient experiences an infusion reaction prior to completion of the infusion, the infusion must be stopped, and the patient should be promptly managed and monitored according to signs and symptoms, and local clinical protocol until there is a complete resolution of the event.

Symptoms of infusion reactions may include: fever, chills, rigors, urticaria, hypotension and hypertension with headache, wheeze, breathlessness, hypoxia, and pulmonary infiltrates. For patients whose infusion-associated events were either Grade 1 or 2, and completely resolved on the day of the infusion, the infusion may be resumed at the discretion of the Investigator at a slower rate with premedication. All subsequent infusions for that patient should then be administered at the reduced rate of infusion with pre-medications. Pre-medications may include medications such as corticosteroids, diphenhydramine, acetaminophen and/or bronchodilators as indicated. FPT155 will be permanently discontinued for patients who have experienced Grade 3 (lasting longer than 4 hours) or above infusion -associated AEs, and for patients who have recurrent infusion-associated reactions after restarting the infusion despite pre-medications and slower infusion.

If a patient experiences an infusion reaction, the patient's vital signs (temperature, blood pressure, pulse, and respiration rate) should be monitored during the infusion, as well as every 30 minutes after the infusion for a minimum of 2 hours and until resolution of the infusion reaction.

### 6.9.6.2 Pembrolizumab

Dose modifications for pembrolizumab will be allowed in accordance with the local [Keytruda® package insert](#). Dose reductions for pembrolizumab are not permitted.

Pembrolizumab may cause severe or life-threatening infusion-reactions including severe hypersensitivity or anaphylaxis. Signs and symptoms usually develop during or shortly after drug infusion and generally resolve completely within 24 hours of completion of infusion. Dose modification and toxicity management for infusion reactions associated with pembrolizumab should be in accordance with the guidelines provided in the [Keytruda® USPI](#).

AEs associated with pembrolizumab exposure may represent an immunologic etiology. These irAEs may occur shortly after the first dose or several months after the last dose of pembrolizumab treatment and may affect more than one body system simultaneously. irAEs may be managed with interruptions of pembrolizumab, administration of corticosteroids and/or other supportive care. Dose modification and toxicity management for irAEs associated with pembrolizumab should be done in accordance with the guidelines provided in the local Keytruda® package insert.

### 6.10 Treatment After the End of the Study

At the end of the study, the Sponsor will not continue to provide Sponsor-supplied study intervention to patients/investigators unless the Sponsor extends the study. The investigator should ensure that the patient receives appropriate standard of care to treat the condition under study.

## 7.0 DISCONTINUATION OF STUDY INTERVENTION AND PATIENT DISCONTINUATION/WITHDRAWAL

### 7.1 Discontinuation of Study Intervention

See the Schedule of Assessments ([Table 1](#), [Table 2](#), [Table 3](#), and [Table 4](#)) for data to be collected at the time of treatment discontinuation and for any further evaluations that need to be completed.

Study treatment may be discontinued for any of the following reasons:

- Consent withdrawal at the request of the patient or their legally authorized representative
- Progressive disease as assessed by the investigator. Treatment beyond disease progression may be allowed in select patients in accordance with Section [4.3](#).
- Any event that would pose an unacceptable safety risk to the patient
- A concurrent illness that would affect assessments of the clinical status to a significant degree
- A positive pregnancy test at any time during the study
- Specific request of the Sponsor or its authorized representative (e.g., if the study is terminated for reasons of patient safety)
- AE
- Investigator decision
- Patient decision, non-AE
- Other

